9.2. Setting

Adult patients prescribed a DOAC or warfarin will be selected between July 1, 2013 and December 31, 2017. Patients will be required to have one or more AF diagnosis claim in any position before or on index date. Patients will be required to have health plan enrollment (Parts A and B) for 6 months prior to the index date to ensure availability of complete patient medical history.

Follow-up Period:

The follow-up period will be defined as the time period between the day after the index date and end of study period (December 31, 2017). Patients will be followed from the day after the index date to 30 days after the date of discontinuation, switch, death, end of study period, or end of continuous medical enrollment (Parts A & B), whichever is earlier.

To assess first stroke/SE event, patients will be censored at first stroke/SE occurring anytime during period on the drug or within 30 days from the last day of days' supply of treatment prescription, 30 days after date of discontinuation, switch, death, end of study or end of continuous medical enrollment (Parts A and B), whichever is earlier.

To assess first MB event, patients will be censored at first major bleeding occurring anytime during period on the drug or within 30 days from the last day of days' supply of treatment prescription, 30 days after date of discontinuation, switch, death, end of study or end of continuous medical enrollment (Parts A and B), whichever is earlier.

For patients with stroke/SE or MB event, net clinical benefit will be assessed by evaluating the first hospital claim for a stroke/SE or MB. The hospital claim can occur anytime during the period of drug use or within 30 days from the last day of supply of treatment prescription.

Other Factors Affecting Censoring During Follow-up

Discontinuation

Discontinuation will be defined as no evidence of index OAC prescription for 30 days from the last day of days' supply of last filled prescription. The date of discontinuation will be the last day of days' supply of last filled prescription. The follow-up will be censored at 30 days after the index drug discontinuation date.

Switch

Atrial fibrillation patients that receive a prescription for an OAC (warfarin, apixaban, dabigatran, edoxaban, or rivaroxaban) other than the index drug prescription during the follow-up period will be considered switchers if this OAC prescription is within ± 30 days of last days' supply. The follow-up will be censored at the switching of the index drug.

9.2.1. Inclusion Criteria

Patients must meet all of the following inclusion criteria to be eligible for inclusion in the study:

- Obese or severely obese.
- Initiated an OAC from July 1, 2013 - December 31, 2017; the first DOAC pharmacy claim date during the identification period will be designated as the index date. The first warfarin prescription date will be designated as the index date for patients without any DOAC claim.
- Individuals ≥ 18 years old as of the index date.
- Had 6 months continuous health plan enrollment with medical benefits (Parts A & B) for at least 6 months pre-index date (baseline period).

- At least 1 diagnosis of AF prior to or on index date, identified by any medical claim associated with an International Classification of Diseases, Ninth Revision, Clinical Modification (ICD-9-CM) code of 427.31 or International Classification of Diseases, Tenth Revision, Clinical Modification (ICD-10-CM) code of I480-I482, and I4891.
- Had body weight or BMI value reported within ± 6 months of the index date.

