NON-INTERVENTIONAL (NI) STUDY PROTOCOL

Study Information

Title	Effectiveness and Safety of Oral Anticoagulants Among Obese Patients with Non-Valvular Atrial Fibrillation in the Veterans Affairs Population with Medicare
Protocol number	B0661162
Protocol version identifier	1.0
Date	September 14, 2020
Active substance	N/A
Medicinal product	Apixaban
Research question and objectives	
The primary analysis will compare apixaban vs warfarin only.
 
Primary Objectives:
 
Aim 1: Evaluate the demographics and clinical characteristics of obese and severely obese NVAf patients initiating OACs (all patients, standard dose, and low dose).
 
Aim 2: Determine if there is a difference in OAC treatment effect between obese and non-obese and severely obese and non-severely obese patients for stroke/systolic embolism (SE), MB, and net clinical benefit.
 
Aim 3: Compare the risk of stroke/SE, major bleeding, net clinical benefit among obese and severely obese NVAf patients initiating OACs.

Author	PPD [REDACTED] PPD [REDACTED] PPD [REDACTED] PPD [REDACTED] PPD [REDACTED] PPD [REDACTED]
---------------	--

This document contains confidential information belonging to Pfizer. Except as otherwise agreed to in writing, by accepting or reviewing this document, you agree to hold this information in confidence and not copy or disclose it to others (except where required by applicable law) or use it for unauthorized purposes. In the event of any actual or suspected breach of this obligation, Pfizer must be promptly notified.

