4. ABSTRACT

Title: Effectiveness and Safety of Oral Anticoagulants Among Obese Patients with Non Valvular Atrial Fibrillation in the Veterans Affairs Population with Medicare

Rationale and Background: Prior RWD studies have evaluated the use of oral anticoagulants (OAC) in obese patients with atrial fibrillation (AF), but they are limited by sample size or by using ICD-9 diagnosis codes to define obesity. Conducting analyses of different datasets and addressing some of these limitations could add important information about the use of OACs in this population.

Research Question and Objectives: The overall objective of this analysis is to understand patient characteristics, use of treatment, and clinical outcomes among obese and severely obese patients with non-valvular atrial fibrillation (NVAf) who initiate therapy with OACs. The aim of this study is to compare all DOACs to warfarin; however, the primary analysis will be conducted among apixaban vs warfarin patients only. If sample size permits, we will also conduct other DOAC vs warfarin and DOAC vs DOAC analysis.

Study Design: This retrospective observational study will be conducted using linked national patient-level data from the Veterans Affairs (VA) Population and Center for Medicare and Medicare Services (CMS) fee-for-service database. The study period will be from January 1, 2013 through December 31, 2017. The study allows for a 6-month baseline period prior to the index date in the identification period. The index date will be defined as the date of first prescription for an OAC from July 1, 2013 – December 31, 2017; the first direct oral anticoagulant (DOAC) pharmacy claim date during the identification period will be designated as the index date. The first warfarin prescription date will be designated as the index date for patients without any DOAC claim. Patients will be required to have ≥ 1 AF medical claim in any position in the inpatient or outpatient setting before or on the index therapy date. Patients will be followed from the day after the index date until the earliest of 30 days after the date of discontinuation, switch, death, end of study period, or end of continuous medical enrollment (Parts A and B).

Population: Obese or severely obese AF patients in the CMS Medicare and Veterans' Health Affairs (VHA) databases who were newly prescribed OACs between January 1, 2013 and December 31, 2017.

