8.1.1. Primary Objectives

Aim 1: Evaluate the demographics and clinical characteristics of obese and severely obese NVAf patients initiating OACs (all patients, standard dose, and low dose; primary analysis will compare apixaban vs warfarin).

Aim 2: Determine if there is a difference in OAC treatment effect between obese and non-obese and severely obese and non-severely obese patients for stroke/SE, MB, and net clinical benefit.

Aim 3: Compare the risk of stroke/SE, MB, net clinical benefit among obese and severely obese NVAF patients initiating OACs (primary analysis will compare apixaban vs warfarin).

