8.1.2. Secondary Objectives

Aim 4: A secondary analysis will also evaluate the following among warfarin treated obese and severely obese patients:

- Distribution of international normalized ratio (INR; <2, 2-3, >3).
- Distribution of time in therapeutic range (TTR \geq 65% [good] and TTR <65% [poor]).
- Compare the baseline characteristics of patients with good vs poor TTR.

CCI

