9.2.3. Cohorts

After applying the selection criteria, patients will be assigned to the following subgroups based on body weight and BMI measures:

1. Obese Patients: Patients with body mass index (BMI) ≥ 30 or body weight ≥ 100 kg within ± 6 months from the index date.
2. Non-Obese Patients: Patients not categorized as obese patients i.e. BMI < 30 or body weight < 100 kg patients within ± 6 months from the index date will be designated as non-obese patients.
3. Severely Obese Patients: Patients with BMI > 40 or body weight > 120 kg within ± 6 months from the index date.

4. **Non-Severely Obese Patients:** Patients not categorized as Severely Obese ie, BMI \leq 40 or body weight \leq 120 kg patients within \pm 6 months from the index date will be designated as non-severely obese patients.²⁴

For patients that have multiple body weights during \pm 6 months from the index date, the body weight closest to the index date will be used. Also, BMI will be given a preference over body weight in identifying patients into the above categories.

For each of the proceeding subgroup, patients will be categorized into the following cohorts based on their index OAC:

- a. Apixaban Cohort;
- b. Dabigatran Cohort;
- c. Edoxaban Cohort;
- d. Rivaroxaban Cohort;
- e. Warfarin Cohort.

The descriptive analysis will also be conducted separately among patients with low and standard dose OACs, defined below in [Section 9.3 Variables](#).

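### Obesity is a study-level inclusion criterion, so the obese versus non-obese half of primary Aim 2 has no comparator as written

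*Combined protocol and SAP*

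**What the plan says.** - **Selection (9.2.1).** All listed criteria must be met. The first is "Obese or severely obese". The last asks only that a measurement exists: "Had body weight or BMI value reported within" six months either side of the index date.
- **Abstract, Population.** The same restriction appears: "Obese or severely obese AF patients in the CMS Medicare" and VHA databases.
- **Cohorts (9.2.3).** "After applying the selection criteria, patients will be assigned to the following subgroups based on body weight and BMI measures". Four groups follow: obese (BMI ≥ 30 or weight ≥ 100 kg), non-obese, severely obese (BMI > 40 or weight > 120 kg) and non-severely obese. The non-obese group is given as "Patients not categorized as obese patients i.e. BMI < 30 or body weight < 100 kg patients". BMI takes precedence over weight when patients are placed in these groups.
- **Objectives (Study Information and 8.1.1).** Aim 2, listed as primary: "Determine if there is a difference in OAC treatment effect between obese and non-obese and severely obese and non-severely obese patients", for stroke/SE, major bleeding and net clinical benefit.
- **Analysis (9.7.1).** Three sets of inverse probability weights are planned: one for all patients, one for obese patients and one for severely obese patients. The Cox models are to carry a treatment-by-obesity-status term, which the text ties to the secondary objective.
- **Secondary objective (8.1.2).** The only visible aim begins "A secondary analysis will also evaluate the following among warfarin treated obese and severely obese patients" and concerns INR and TTR. Parts of 8.1.2 and 9.7.2 are redacted.

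No visible passage exempts Aim 2 from the obesity criterion.

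**The concern.** An interaction between treatment and obesity needs patients at both levels of obesity. The selection rule admits one level, and the subgroups are formed only after it has been applied. A programmer who follows 9.2.1 and one who follows 8.1.1, 9.2.3 and 9.7.1 would build different study populations from the same protocol. At stake is half of a primary aim, and the breadth of the reference group in the other half.

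**Working it through.** The documents state no figure to reproduce here. The check applies 9.2.1 and then 9.2.3, using only the cut-offs in 9.2.3.

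**1. The criterion reduces to obese.** BMI > 40 implies BMI ≥ 30, and weight > 120 kg implies weight ≥ 100 kg. Every severely obese patient is therefore obese, and the first inclusion criterion admits exactly the obese.

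**2. Non-obese patients after selection.** Under the precedence rule each patient has one label: by BMI where there is one, by weight where there is none. Selection keeps those labelled obese, and the non-obese are those not so labelled. The overlap is empty: **0 patients**. As a mechanical check, the rules were run on a grid of 64 BMI-by-weight combinations (cells, not patients). On either measure, 55 cells met the obese definition, and 0 of the 55 were non-obese as its complement. With BMI deciding, the count was again 0.

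**3. The interaction.** Write the log hazard ratio part as βT + γZ + δTZ, with T for treatment and Z for obesity. If Z = 1 for everyone, TZ = T, so β and δ cannot be separated. δ is the quantity Aim 2 asks for in its obese versus non-obese half.

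**4. The weighting sets.** If everyone selected is obese, the set for all patients equals the set for obese patients. Three planned sets become two.

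**5. Severe versus non-severe.** Both levels remain. In the grid, 24 included cells were non-severe with BMI deciding. The reference group changes:

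| Basis | Non-severe as defined in 9.2.3 | Non-severe left after 9.2.1 |
|---|---|---|
| BMI available | BMI ≤ 40 | BMI 30 to 40 |
| Weight only | ≤ 120 kg | 100 to 120 kg |

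**6. Could a looser reading rescue the comparator?** Suppose, against the precedence rule, that inclusion could be met on weight alone and patients were then classified on BMI. A non-obese patient would need weight ≥ 100 kg and BMI < 30, hence height > √(100/30) = 1.826 m. The qualifying weights are 100 to 102.7 kg at 1.85 m (30 × 1.85² = 102.7) and 100 to 108.3 kg at 1.90 m (30 × 1.90² = 108.3). BMI < 25 would need height > √(100/25) = 2.00 m. Such a group holds only tall, heavy patients and is not a usable non-obese comparator.

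**7. What the rest of the protocol implies.**
- Table 1 has five BMI categories, three of them below 30. Under step 2 those three would be empty among patients with a BMI.
- The feasibility population in 9.5 (about 56,000, of whom 20,000 on apixaban) is described by NVAF and a reported BMI or weight. No obesity restriction is mentioned.
- The checklist in 9.8 asks that subgroups add up to the total population for interaction. This is weaker evidence, since the same list refers to five databases and looks partly generic.
- The last criterion in 9.2.1 adds nothing if the first applies, because being classed as obese already requires a BMI or weight value. That is redundancy, not a contradiction in itself.

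**The case against.** The best answer is that the intent is plain. Aim 2, the non-obese cohort, the weights for all patients, the low BMI categories and the feasibility description all presuppose non-obese patients. A programmer who applied 9.2.1 literally would meet an empty cohort and two identical weighting sets, so the error would reveal itself and is unlikely to bias a result silently. That stands, and it is why this is best read as a drafting error. It does not cure the text: 9.2.1 is the operative rule, the abstract repeats it, and nothing says which passage governs.

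Four stronger readings are tempting but not supported.

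- **Patients counted on both sides of the contrast.** A reader might infer this from the loose gloss in the non-obese definition. A patient of 1.75 m and 95 kg (95/1.75² = 31.0) fits the wording of both groups, as does one of 1.88 m and 102 kg (28.9). For severe obesity the same holds at 1.80 m and 125 kg (38.6) and at 1.68 m and 115 kg (40.7). But the main clause already makes each group a complement, and BMI precedence gives each example one label: obese, non-obese, non-severe and severe in turn. With weight alone, the two sides cannot overlap. The gloss needs tidying; no double counting follows.
- **All of Aim 2 fails.** It does not. The severe versus non-severe contrast can be estimated, against a narrower reference.
- **The interaction has been demoted to a secondary analysis.** Section 9.7.1 does tie it to the secondary objective while Aim 2 is listed as primary. With 8.1.2 and 9.7.2 partly redacted, the documents support only a request to reconcile the two.
- **A count of patients lost.** The obese share of the roughly 56,000 is not given, so none can be derived.

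**Conclusion.** The contradiction is real and must be fixed before the study population is built. Section 9.2.1 and the abstract conflict with Aim 2, with the non-obese cohort in 9.2.3, and with the weighting sets and interaction in 9.7.1. Its effect is total for one half of a primary aim (no comparator) and partial for the other (a narrowed reference). The conclusion rests on reading 9.2.1 literally and on the BMI precedence in 9.2.3; it uses no outside figure and no assumed effect size. It makes no claim about redacted text.

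**What to change.** 1. **9.2.1:** remove obesity from the study-level criteria and keep the requirement for a BMI or weight value.
2. **Analysis sets:** apply the obesity restriction to Aims 1, 3 and 4 only, and define the Aim 2 set as all eligible patients.
3. **Abstract (Population), Section 7 (study goal) and Section 8.1 (overall objective):** align the wording, which is framed around obese and severely obese patients only.
4. **Wording note, 9.2.3:** bring the glosses on the non-obese and non-severely obese groups into line with the section's own complement and BMI-precedence rule.
5. **Wording note, 9.7.1:** reconcile the reference to the secondary objective with the listing of Aim 2 as primary.

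The cost is text only. The study is retrospective on an existing linked database, so no new data source is needed. If a cohort has already been extracted under the literal rule, the extraction would have to be rerun.

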9. RESEARCH METHODS

9.1. Study Design

9.1.1. Key Index Period Definitions

[figure not shown]
- **Study Period:** The study period will range from January 1, 2013 through December 31, 2017.
- **Patient Identification Period:** The identification period will range from July 1, 2013 until December 31, 2017, allowing for a 6-month baseline period prior to the index date.
- **Baseline Period:** The baseline period will be 6 months prior to, and on, the index date.
- **Follow-up Period:** The follow-up period will be defined as the time period between the day after the index date and end of study period (December 31, 2017). Patients will be followed from the day after the index date to 30 days after the date of discontinuation, switch, death, end of study period, or end of continuous medical enrollment (Parts A & B), whichever is earlier.

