9.3. Variables

Baseline variables during the 6 months prior to, and on, the index date will be measured. Baseline variables will be evaluated using codes in any position unless noted otherwise.

Table 1. Baseline Demographic and Clinical Characteristic Variables

Variable	Data Source(s)	Operational Definition
Age	Both VA and Medicare	Age will be defined as of the index date and used to assign patients to age groups (eg, 18-54, 55-64, 65-74, 75-79, \geq 80 years).
Sex	Both VA and Medicare	A flag will be created for female beneficiaries and reported as a percentage.
US Geographic Region	Both VA and Medicare	The United States will be divided into 5 regions: Northeast, South, Midwest, West, and Other.
Race	Both VA and Medicare	Race will be identified and will be categorized as: White, Black, Other, and unknown.
Year of index OAC	Both VA and Medicare	A flag will be created for proportion of unique patients with index OAC identified in 2013, 2014, 2015, 2016, and 2017.

Variable	Data Source(s)	Operational Definition
Dose of Index DOAC	Both VA and Medicare	-Standard dose (apixaban 5 mg, dabigatran 150 mg, and rivaroxaban 20 mg) based on dose of the initial prescription of DOAC; -lower dose (apixaban 2.5 mg, dabigatran 75 mg, rivaroxaban 15 mg/10 mg) based on dose of the initial prescription of DOAC.
Body Weight	VA	Body weight will be obtained as continuous and categorical variables. The categories will be: ≤ 60 kg, 61-99 kg, 100-119 kg, and ≥ 120 kg. If a patient has multiple values, the value closest to the index date will be used.
BMI	VA	Body Mass Index: Body mass index will be calculated as weight in kilograms divided by the square of height in meters. Mean, median, and standard deviation will be provided for the continuous variable. The categories will be <18.5 , 18.5-24.9, 25-29.9, 30-39, and ≥ 40 . If a patient has multiple values, the value closest to the index date will be used.
Creatinine Clearance	VA	Creatinine Clearance: Creatinine clearance will be identified using LOINC codes (2160-0, 33914-3, 48642-3, 48643-1, 62238-1, 2164-2, 14682-9). A categorical variable for the glomerular filtration rate (GFR) will be created with the following cutoff points: <15 ml/min, 15-29 ml/min, 30-59 ml/min, 60-89 ml/min, and ≥ 90 ml/min. If a patient has multiple values, the value closest to the index date will be used. The creatinine clearance rate (CrCl) will be calculated based on serum creatinine for patients who only had serum creatinine information. ²⁵

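### Obesity status can be set by a weight or BMI recorded up to 6 months after index, so cohort entry and the Aim 2 effect modifier depend on post-treatment information

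*Combined protocol and SAP*

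**What the plan says.** **Eligibility.** Section 9.2.1 lists "Obese or severely obese" as an inclusion criterion and separately requires that the patient "Had body weight or BMI value reported within" 6 months either side of the index date.

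**Classification.** Section 9.2.3 defines all four weight groups over the same two-sided window, for example BMI of at least 30 "or body weight ≥ 100 kg within ± 6 months from the index date". With several weights, "the body weight closest to the index date will be used". The weight and BMI rows of Table 1 carry the same rule: "If a patient has multiple values, the value closest to the index date will be used". Neither place prefers a value taken before index. Weight and BMI come from VA data only.

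**Follow-up.** Section 9.1.1: "Patients will be followed from the day after the index date to 30 days after the date of discontinuation" or another censoring reason.

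**Baseline window.** Section 9.3 opens with: "Baseline variables during the 6 months prior to, and on, the index date will be measured". Section 9.1.1 defines baseline the same way, and Table 1 lists weight and BMI among the baseline variables.

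**A third anchor.** The feasibility count in Section 9.5 used a value within 6 months either side of the index diagnosis, not the index date.

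**The concern.** Obesity status is more than a descriptive covariate here. It is an inclusion criterion, it defines two of the three weighted populations in Section 9.7.1, and it is the modifier in Aim 2, tested by a treatment-by-obesity term in the Cox models. A variable with those roles should be fixed by time zero.

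Under the written rule, two things can happen after time zero:

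- A patient with no pre-index value enters only if weighed in the VA during the following 6 months.
- A patient with an older pre-index value is reclassified if a post-index value lies nearer to index, including one taken after a stroke or bleed.

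Measurement may well differ by arm. Section 7 says that warfarin needs close INR monitoring and that DOACs need fewer routine monitoring visits. Weighting on baseline covariates does not undo selection on later data. The propensity-matched sensitivity analysis in Section 9.7.2, the only one visible in the unredacted text, is not given a different weight window and so inherits the problem. Section 9.9 does not mention it and presents the VA measurements as a strength.

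**Working it through.** **1. Check the follow-up assumptions against the plan's own sample size.** Inputs from Section 9.5: HR 0.63, warfarin rate 1.10 per 100 person-years, alpha 0.05, power 80%, accrual 4.5 years, loss 55% (warfarin) and 40% (apixaban). Neither the time unit of the loss nor the sidedness of alpha is stated. I take annual loss and a two-sided test.

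- Events (Schoenfeld): 4(1.960 + 0.842)² / (ln 0.63)² ≈ 147.1, rounded up to 148.
- With uniform accrual, no added follow-up and exponential loss, 7,945 per arm gives 79.1 + 65.1 = 144.2 expected strokes, or 0.01816 per matched pair.
- Required per cohort: 148 / 0.01816 ≈ 8,152, against 7,945 stated (+2.6%). The same method gives all eight rows of Table 3 within 3%, so the annual reading is reasonable.

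**2. How much outcome time overlaps the post-index window?** Let h = −ln(0.45) = 0.799 for warfarin and −ln(0.60) = 0.511 for apixaban.

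- Mean follow-up = (1/h)[1 − (1 − e^(−4.5h)) / (4.5h)] = 0.913 and 1.19 years (0.91 and 1.18 if strokes also end follow-up).
- The first 6 months hold 43% of warfarin and 35% of apixaban person-time.
- They also hold 34.1 + 23.0 = 57.0 of the 144.2 expected strokes, or 40%.
- Index dates from 1 July to 31 December 2017 (184 of 1,645 days, 11%) have a post-index window cut short by the end of the study period.

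**3. Illustration A: time before weighing treated as event-free.** Assumptions not in the documents: the share of each arm that qualifies only on a post-index value, and a mean delay of 0.25 year. Event-free share of person-time = share × 0.25 / mean follow-up. HR multiplier = (1 − apixaban share) / (1 − warfarin share).

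| Post-index only, warfarin / apixaban | Share of person-time, warfarin / apixaban | HR multiplier |
|---|---|---|
| 20% / 20% | 5.5% / 4.2% | 0.958 / 0.945 = 1.01 |
| 30% / 10% | 8.2% / 2.1% | 0.979 / 0.918 = 1.07 |
| 10% / 30% | 2.7% / 6.3% | 0.937 / 0.973 = 0.96 |

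**4. Illustration B: selection into the cohort, with early events allowed to count.** Let u be the share with no pre-index value, q the chance of a post-index value without an early event, m that chance after an early event, and s the early share of events (0.43 warfarin, 0.35 apixaban). The observed rate in an arm is the true rate times [(1 − u) + u(ms + q(1 − s))] / [(1 − u) + uq]. Again u, q and m are assumed.

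- q = 0.8 warfarin and 0.5 apixaban, m = 0.9 in both, u = 0.20: 1.031 / 1.009 = 1.022.
- Same q, m = 0.3 in both, u = 0.20: 0.984 / 0.955 = 1.031.
- Over u = 5% to 20% and both values of m, a true HR of 1.00 appears as 1.005 to 1.03, and 0.63 as 0.633 to 0.649.
- With equal measurement (q = 0.6, m = 0.9 in both arms), 1.00 appears as 0.999 to 0.995.

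Illustration B covers entry to the cohort only. Neither illustration addresses misclassified obesity status or the interaction test.

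**5. What a pre-index rule does to numbers.** Required N is unchanged. If 5%, 10%, 20% or 30% of patients had only a post-index value, 19,000, 18,000, 16,000 or 14,000 of the 20,000 apixaban patients in Section 9.5 would remain. That count appears to cover all NVAF patients with a weight or BMI, so the obese and severely obese counts are smaller by an unstated amount.

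**The case against.** **Immortal time.** A reader might infer classic immortal-time bias in the outcome. The documents do not support that. Outcomes are first hospitalisations for stroke/SE or major bleeding. Nothing in 9.2.1 or 9.2.3 requires the weight to precede the event or censoring. A patient can have a stroke in month 1, be weighed in month 4, and enter with the stroke counted. Only death before any weighing is ruled out, and death is a censoring reason. This stands. Illustration A therefore overstates that mechanism when it treats all time before weighing as event-free.

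**Upper bounds.** A reader might also take the multipliers as ceilings. They are not. The shares and the 3-month delay are assumed. Weighing at month 6 would make the 20% warfarin case 0.20 × 43% = 8.6% instead of 5.5%.

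**Reclassification after an event is a narrow path.** It needs an early event, a later VA weight nearer to index than any earlier one, and a change that crosses a cut-point. About 34 of 7,945 warfarin patients (0.4%) would have a stroke in the first 6 months. Bleeds add to this, but no rate is given. An event treated in a Medicare hospital may leave no VA weight. This limits the size but does not remove the path. Ordinary weight change and unequal visit frequency need no event at all.

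**Contradiction.** The two-sided window is explicit and repeated, and reads as a specific rule for one variable against a general baseline sentence. The cohort rule itself is not in doubt. Because Table 1 lists weight and BMI as baseline variables, the text still needs reconciling.

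**A sensitivity analysis might be enough.** A pre-index-only sensitivity analysis would show whether the rule matters. But it would leave the primary analysis on the less defensible definition when the better one needs only reprogramming and some loss of patients.

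**Conclusion.** The point holds as selection and classification on post-index data. That follows directly from the text: a value up to 6 months after index can admit a patient or set the subgroup, and follow-up has already begun.

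Size and direction cannot be derived, because the share of patients whose only or closest value is post-index is not given, overall or by arm. Under the assumed shares with unequal measurement, the main HR shifts by about 0.5% to 7%. The low end is more plausible, since the 7% needs a 30% versus 10% split and treats time before weighing as event-free. With equal measurement the shift is 0.1% to 1.4%. The effect on the Aim 2 interaction has not been quantified. All figures rest on annual loss, which Section 9.5 does not state but which reproduces Table 3. The documents do not support a claim that the plan is biased towards either drug.

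**What to change.** 1. In 9.2.1 and 9.2.3, assign eligibility and obesity status from the last weight or BMI on or before the index date, using the plan's own baseline window (6 months before, and on, index). Apply the same rule to the weight and BMI rows of Table 1.
2. Keep the two-sided 6-month definition as a named sensitivity analysis for Aims 2 and 3.
3. Report, by arm, the share of patients whose only value, and whose closest value, is post-index.
4. Reconcile the baseline window in 9.1.1 and 9.3, the window around the index date in 9.2.1 and 9.2.3, and the window around the index diagnosis in 9.5.

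The cost is protocol wording, reprogramming, and the loss of patients with only post-index values from the primary analysis. The remaining obese and severely obese counts should be checked by arm against Table 3 before the change is final. A longer look-back for this variable (for example 12 months) is optional. It recovers some patients but admits older weights. Because the study period starts on 1 January 2013, patients indexed in July to December 2013 would need vitals extracted from before that date.
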